- Prospective participants <18-years or >89-years of age;
- Presently incarcerated or in police custody;
- Non-English speaking;
- Critically-ill;
- Intoxicated with alcohol or other substances;
- ED staff objected against entering room;
- Unwilling or unable to complete the safety plan electronically;
- Unwilling or unable to use a tablet;
- Unwilling or unable to show/email this safety plan to clinical and research staff.

Title: Written safety planning vs the Safety Net app: A prospective randomized pilot trial

PI: [name], PhD

Site: University of Arkansas for Medical Sciences

If participants indicate interest in the study and meet all inclusion/exclusion criteria, informed consent will be obtained using IRB-approved consent forms & processes. If they provide consent, participants (n=30) will be randomized in a 1:1 fashion to either the traditional written safety plan group, in which they will complete a written safety plan with a peer support specialist or other research staff member, or the electronic "Safety Net" safety plan group, in which they will complete an electronic safety plan with a peer support specialist or other research staff member (please see Figure 2 above).

Participants will be randomized using the randomization function in REDCap. All participants will be allowed to complete the safety plan in the privacy of their ED treatment room. Please note that participants will be given a \$25 gift card for participating regardless of which group they are randomized into for the study.

After completing the safety planning process, participants will then be asked to answer a short questionnaire concerning their demographics (e.g., age, biological sex), any history of previous suicidal ideation, suicide attempts, or related behaviors, and satisfaction with the safety planning process.

Regardless of whether the safety plan is completed in the traditional paper format or electronically, this will be shown to the UAMS ED psychiatric registered nurse or social worker for approval and entry into the EMR. Please note that the study will not otherwise modify care in the ED. It is possible, although not likely, that psychiatry consultants could choose to revise, edit, or otherwise start anew with safety planning for a particular patient. If so, the patient will be withdrawn from the study.

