Other measures: All participants will complete a brief questionnaire regarding their demographics, history of suicidal behaviors, and satisfaction with the safety planning process. After the visit, the electronic medical record will be searched for the following data: date/time of ED triage and disposition; length of ED stay; ED chief complaint or reason for visit; patient disposition (observation/admission/discharge/transfer); psychiatric diagnoses; and frequency of ED visits 3 months before and after the intervention. Length of ED stay will be compared against two control groups (obtained using AR-CDR): a) length of stay of all ED patients during a similar time period; and b) length of stay of ED patients who presented for SI during a similar time period. No PHI will be recorded for either of these deidentified control groups. Peers and other research staff will also be asked to record the total amount of time that they spent performing the safety plan intervention.

Study retention: The study duration is limited to the ED visit (typically <6 hours for SI patients), with participation in the study limited to the interventions mentioned above. Consequently, no special measures designed to increase retention are planned.

Title: Written safety planning vs the Safety Net app: A prospective randomized pilot trial
PI: [name], PhD
Site: University of Arkansas for Medical Sciences

Recruitment of peers for this project

Peers will be recruited through existing relationships with community suicide prevention organizations (i.e., Arkansas Foundation for Suicide Prevention, Arkansas Governor's Suicide Prevention Council, Veterans Service Organizations, etc.). Eligible recruits will complete an interview with [name] where they will be informed about the responsibilities and expectations of working with this project. Training and supervision of peers and other research staff will be used to further monitor the appropriateness of the individual to assist patients in providing the intervention.

Training of peers and other nonclinical individuals

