As a licensed clinical counselor, [name] will assess the provider's skill level and will become the role of a teacher, counselor, or consultant based on need. In other words, peers and mental health staffs will be provided with either instruction and direct feedback (i.e., the teacher role), support for reflection and processing of personal experiences (i.e., the counselor role), or encouraging confidence in required skills (i.e., the counselor role) depending on need.

In terms of direct supervision, [name] will be on site during the first week of the intervention to observe performance and operation. She will ensure that the safety plan is being administered, documented, and managed appropriately by each provider (see also "Fidelity of the intervention" below). If deficits are identified, she will work with individuals to make needed improvements. During the first week of intervention implementation, [name] will also conduct an individual face-to-face interview with each peer. Interview questions will be guided by the Consolidated Framework for Implementation Research (CFIR)¹⁹ and focus on identifying and overcoming perceived barriers to implementation of the intervention.

Peers will also be provided with clear instructions on how to obtain help during any difficult or uncomfortable situations during the intervention. After the first week of the intervention, peers may inform ED clinical staff (social worker or psychiatric nurse) on site of such situations so that the staff may continue working on the safety plan with the participant. ED clinical staff are available 24/7 so peers would not have much trouble in finding and asking someone for help with a participant during these situations. Participants who do not complete the safety planning with a peer will be withdrawn from the study, but peers will be informed that their safety and well-being remains a priority when completing the intervention and so they should not hesitate to ask clinical staff for help. Peers may also contact [name] using the contact information provided during

Title: Written safety planning vs the Safety Net app: A prospective randomized pilot trial
PI: [name], PhD
Site: University of Arkansas for Medical Sciences

peer training in order to schedule an in-person meeting. [name] will debrief the peer at these meetings by further discussing the difficult or uncomfortable situations.

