Measurement of safety plan quality: All safety plans will be evaluated by existing ED clinical staff for approval. If it needs to be modified, it will be documented that the research staff had to gather more information from the participant. Safety plans will also later be graded on a numerical rating scale (0-2 or 0-3, depending on grading component) by the investigators using materials developed by Gamarra et al for this purpose.²⁰ Using a “safety checklist,” responses for each of the 6 safety plan steps (with step 3 divided into two parts) and the “most important thing worth living for” section will be rated according to the personalization of the information in each section. In addition, each section will be independently rated for “completeness” (0=not complete, 1=partially complete, 2=complete) and “quality” (0=blank, 1=boilerplate, 2=some evidence of personalization, 3=highly personalized and specific). For instance, in the answer to the question “Warning signs (list 3 items),” patients may simply list “sad” which reflects a low-quality answer. Alternatively, the patient may answer “Feeling like I can’t stop crying or can’t stop being sad” which reflects a higher-quality more personalized answer. Each of the sections in a participant’s safety plan will be graded in this manner, with completeness having a maximum score of 16 and quality having a maximum score of 24. An overall score for the safety plan will be derived by adding the scores for all sections in a participant’s safety plan. Peers and other nonclinical individuals will be trained to coach participants towards higher-quality answers (please see above).

Monitoring: Adverse events or in case of psychiatric emergency

By definition, all patients have presented to the ED for an acute mental health crisis and will be under the care of trained ED physicians, trained ED nurses, trained

Title: Written safety planning vs the Safety Net app: A prospective randomized pilot trial

PI: [name], PhD

Site: University of Arkansas for Medical Sciences

psychiatric ED nurses who typically complete the safety plan, and other psychiatric personnel as appropriate. In the unlikely event of psychiatric decompensation, peers will be instructed to stop the intervention and seek help from qualified personnel in the ED. The intervention will then not be continued.

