Title: Written safety planning vs the Safety Net app: A prospective randomized pilot trial
PI: [name], PhD
Site: University of Arkansas for Medical Sciences

once the study is complete. If so, electronic records will be audited to ensure high fidelity with the originals. These electronic copies will also be maintained on secure password-protected UAMS servers. When eventually destroyed, copies will be shredded per UAMS disposal guidelines.

Data collection will be performed through the Research Electronic Data Capture (REDCap) system on a secured UAMS wireless network, and it will be set up in cooperation with the UAMS Translational Research Institute (TRI) in order to assure 21 CFR Part 11 and HIPAA compliance.

Data Analysis

Outcome measures: Number of patients approached who agree to allow trained non-clinical staff to assist them with safety planning (if they do not agree, no other information about the patient will be recorded); the number of patients approached who meet all inclusion/exclusion criteria (if patients are not eligible for the study, no other information about the patient will be recorded); the number of participant safety plans which must be redone either by the peer support specialist, other nonclinical individuals, or clinical staff; the quality of completed safety plans; and patient satisfaction with each method.

Outcome 1: Evaluate the proportion of SI patients approached in the UAMS ED who agree to allow trained non-clinical staff to assist with safety planning. This number is currently unknown.

Outcome 2: Evaluate the proportion of patients approached who meet all inclusion/exclusion criteria. This number may be lower than the number of patients willing to participate in safety planning.

Outcome 3: Evaluate the quality of the completed safety plans. This will be done by retrospective review after the patient has left the ED. The number of safety plans that must be repeated or redone by clinical providers will also be tracked.

Outcome 4: Patient satisfaction with each method. This will be assessed by having the patient rate their experience with the safety planning process on a 7-point Likert scale (*strongly disagree; disagree; moderately disagree; neutral; moderately agree; agree; strongly agree*).

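### Withdrawing randomised participants who do not finish the plan with a peer turns Outcomes 3 and 4 into a comparison of completers, and non-completion is not reported by arm

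*Combined protocol and SAP*

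**What the plan says.** All references are to the combined protocol and SAP.

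- **Study Design and Procedures**, after the exclusion criteria: participants consent, are randomised 1:1 (n=30) and make their plan with a peer or another research staff member. Then: "After completing the safety planning process, participants will then be asked to answer a short questionnaire concerning their demographics". The same questionnaire covers suicidal history and satisfaction.
- **Other measures**: "All participants will complete a brief questionnaire regarding their demographics, history of suicidal behaviors, and satisfaction with the safety planning process". No time point is given, and nothing is said about those who stop early.
- **Supervision and debriefing of peers**, in the paragraph on how peers obtain help: "Participants who do not complete the safety planning with a peer will be withdrawn from the study".
- **Monitoring: Adverse events**: if a patient decompensates, the peer stops and seeks help. "The intervention will then not be continued". The section does not mention withdrawal or outcome collection.
- **Measurement of safety plan quality**: "each section will be independently rated for “completeness” (0=not complete, 1=partially complete, 2=complete". Quality runs from 0 (blank) to 3.
- **Data Analysis**: "Outcome 3: Evaluate the quality of the completed safety plans". Outcome 4 is obtained by "having the patient rate their experience with the safety planning process on a 7-point Likert scale". The number of redone plans is also tracked. No analysis population is defined, and no rule is given for the data of withdrawn participants.

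A separate rule covers finished plans that are later changed: "psychiatry consultants could choose to revise, edit, or otherwise start anew with safety planning for a particular patient. If so, the patient will be withdrawn". That is a different event from not finishing with the peer.

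**The concern.** Completion is determined after randomisation, and the assigned format could influence it. If participants who do not finish are withdrawn, and satisfaction and plan grades come only from those who do, the two arms are no longer the groups that were randomised. If non-completion differs between arms, the arm with more of it loses observations that are likely to be low.

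The information lost is also part of what the pilot sets out to learn. The third research question in the introduction asks whether ED patients will complete plans electronically. A patient randomised to the app who does not finish is direct evidence on that question, yet none of the listed outcomes counts such patients by arm.

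The questionnaire also collects demographics and suicidal history. The analysis section uses age, sex and prior attempts to compare the groups and decide on adjustment, so a participant who misses the questionnaire may drop out of that check as well.

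**Working it through.** **Step 1. The plan's own figures.** Graded sections: 6 steps, plus 1 because step 3 is split, plus 1 for the item on what is worth living for, giving 8. Completeness maximum: 8 × 2 = 16. Quality maximum: 8 × 3 = 24. Both agree with the protocol. The scale therefore already has values for an unfinished plan.

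**Step 2. The rules side by side for a participant who stops.**

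| Section | Effect on a participant who stops |
|---|---|
| Study Design and Procedures | Questionnaire follows completion |
| Other measures | Questionnaire for all participants |
| Supervision and debriefing of peers | Withdrawn from the study (sessions with a peer) |
| Monitoring | Intervention stopped; status in the study not stated |
| Data Analysis, Outcome 3 | Completed plans assessed |

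The second row does not sit easily with the first and third. Nothing in the text says which prevails.

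**Step 3. Size within one arm.** The documents give no non-completion rate and no expected scores, so everything here is assumed except the arm size, 30/2 = 15. The seven satisfaction categories are taken as 1 to 7. With *m* non-completers, completer mean *c* and non-completer value *f*:

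mean over all randomised = [(15 − m) × c + m × f] / 15

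shift from leaving them out = m × (c − f) / 15

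| Measure | c | f | m=1 | m=2 | m=3 | m=4 |
|---|---|---|---|---|---|---|
| Satisfaction (of 7) | 6 | 1 | 0.33 | 0.67 | 1.00 | 1.33 |
| Satisfaction | 6 | 2 | 0.27 | 0.53 | 0.80 | 1.07 |
| Satisfaction | 6 | 3 | 0.20 | 0.40 | 0.60 | 0.80 |
| Completeness (of 16) | 14 | 0 | 0.93 | 1.87 | 2.80 | 3.73 |
| Completeness | 14 | 4 | 0.67 | 1.33 | 2.00 | 2.67 |
| Completeness | 15 | 8 | 0.47 | 0.93 | 1.40 | 1.87 |

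Example: (12 × 6 + 3 × 2)/15 = 5.2 against 6.0 in completers.

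**Step 4. Effect on the between-arm difference.** With equal *c* and *f* in both arms, the difference shifts by (m₁ − m₂) × (c − f)/15. Equal numbers cancel. With 3 non-completers in one arm and 1 in the other, c = 6 and f = 2, the completer means are equal (6.0 and 6.0), while the all-randomised means are 5.20 and 5.73, a difference of 0.53 points.

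**Step 5. Chance that the rule is used at all.** P(at least one non-completer among 30) = 1 − (1 − p)³⁰. For assumed rates p = 5%, 10% and 20% this is 78.5%, 95.8% and 99.9%.

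**The case against.** The strongest counter-argument is that Other measures states a universal rule: all participants answer the questionnaire. On that view, Study Design and Procedures only describes the usual order of events. This stands in part. The text does not establish that a non-completer never receives the questionnaire. But no procedure supports collecting it from someone who has been withdrawn, so the sections still need reconciling.

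A reader might infer that Outcome 4 and the completeness scores miss the people for whom a format failed. The documents do not support that:

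- The withdrawal sentence closes a paragraph on situations that are difficult for the peer, and it names peers only. No rule is stated for sessions run by other research staff. The wording reaches any non-completion with a peer, but the cause need not be paper or app.
- The Monitoring section stops the intervention on decompensation and does not say that the participant is withdrawn. That is a clinical event, not abandonment of a format.
- People unwilling or unable to complete the plan electronically or use a tablet are excluded before randomisation, which removes the plainest route to failure in the app arm.

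Nor is it certain that every unfinished plan goes ungraded. The quality section says that all plans are evaluated by ED staff and provides scores for blank or partial sections, and completed in Outcome 3 could mean filled in. Redone plans are counted too. These points keep part of the signal. They do not restore the satisfaction rating of a withdrawn participant or produce a count of non-completion by arm.

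Figure 2 (study flow) was not available in the text and may say more about participants who stop. Finally, this is a 30-patient pilot, and Outcomes 1 and 2 are settled before randomisation and are unaffected.

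**Conclusion.** The concern holds in a limited form. The withdrawal of participants who do not complete planning with a peer is a stated rule, not a gap. Applied together with the placing of the questionnaire and the wording of Outcome 3, it makes the between-arm comparison of satisfaction and plan quality a comparison of completers. It also leaves non-completion by arm unreported, although a research question turns on it. For participants who stop, the sections on the questionnaire and on withdrawal conflict or are at best ambiguous.

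The size is unknown. About 0.2 to 0.3 satisfaction points and 0.5 to 0.9 completeness points per omitted participant rest on 15 per arm and the assumed scores above. They describe one arm. The difference between arms is distorted only so far as the number of non-completers, or the gap between their scores and those of completers, differs by arm, and the documents give no evidence on either. The pre-randomisation exclusions should keep the numbers low. The change is worth making because the exclusion is avoidable and cheap to remove, not because a large bias has been shown.

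**What to change.** Leave the clinical handover and stopping procedures as they are, and change only what happens to the study data.

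1. **Supervision and debriefing of peers**: say that a participant who does not finish with the peer stops study coaching but stays in the study for data collection and is analysed in the randomised arm. State whether the same holds when another research staff member is coaching.
2. **Study Design and Procedures** and **Other measures**: reconcile the two, so that the existing questionnaire is offered to every randomised participant who is willing and well enough, whether the plan was finished, stopped or handed over.
3. **Measurement of safety plan quality** and **Outcome 3**: grade the plan as it stood when study coaching stopped, using the existing completeness values of 0 or 1 for unfinished sections and quality 0 for blank ones.
4. **Data Analysis**: report non-completion and withdrawal, with reasons, by randomised arm. Make the analysis as randomised the main one, with completers only as a sensitivity analysis.

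The cost is wording in these sections. No new instrument, staff or visit is needed. A copy of the unfinished plan must be kept before clinical staff carry on with it, since the tablet is cleared between patients. Some who stop will decline the questionnaire, so some satisfaction data will still be missing; the number should be shown by arm.

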Site: University of Arkansas for Medical Sciences

adverse events are not expected as a result of this intervention, the PI will carefully monitor for any such event and report any adverse event to the IRB. In addition, if a peer has a relapse or any psychiatric emergency during the course of the intervention, they may contact [name] using the contact information provided during peer training. After this initial contact, [name] will debrief the peer by meeting with them and further discussing the situation.

Please note that although peers will receive mandatory confidentiality training required at the study institution, there is little concern that peers will “say the wrong thing” or break a patient’s confidentiality. Given that these peers have personal experience of hospitalization, it is more likely that they will be willing to guard the patient’s confidentiality and less likely than clinical staff to make insensitive remarks to a patient. However, all peers will be CITI-certified, with periodic reminders about patient confidentiality from the investigators.

Figure 1: Suicide safety planning training cycle

Description of interventions

Written safety plan: Please see separate upload for the Stanley et al version of the safety plan. This safety plan contains 6 components, and is completed by the patient themselves. This intervention takes approximately 20-40 minutes to complete. As a former site for the ED-SAFE study,¹² the UAMS ED typically has patients complete safety plans if being discharged. This is typically done by the psychiatric nurse or social worker if they are available, and this individual then places a progress note in the electronic medical record (EMR). These clinical providers must approve all safety plans in this study as peer support specialists and other research staff do not have the ability to place notes in the EMR.

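### Participants whose plan a psychiatry consultant revises or restarts are withdrawn after randomisation, although redone plans are an outcome and no visible text keeps withdrawn participants in the analysis

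*Combined protocol and SAP*

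**What the plan says.** Study Design and Procedures sends each completed plan, paper or electronic, to the ED psychiatric nurse or social worker for approval. It then raises a further possibility: "It is possible, although not likely, that psychiatry consultants could choose to revise, edit, or otherwise" replace the plan. For revision, editing and restart alike, the text ends with the words "start anew with safety planning for a particular patient. If so, the patient will be withdrawn from the study". By that point the participant has been randomised and has completed a plan.

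Supervision and debriefing of peers contains a second withdrawal. In a difficult situation "peers may inform ED clinical staff (social worker or psychiatric nurse) on site of such situations". The stated purpose is a hand-over, "so that the staff may continue working on the safety plan with the participant". Anyone who does not finish planning with a peer then leaves the study. The section on monitoring of adverse events adds a stop for psychiatric decompensation, with no stated analysis status.

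Data Analysis lists among the outcome measures "the number of participant safety plans which must be redone either by the peer support specialist, other nonclinical individuals, or clinical staff". Outcome 3 reads "Evaluate the quality of the completed safety plans" and then "The number of safety plans that must be repeated or redone by clinical providers will also be tracked". The section names chi-square tests and ANOVAs. It gives no analysis set and no rule for data from withdrawn participants.

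**The concern.** A consultant who restarts a plan is clinical staff in the ordinary sense of the words. Where the plan had to be redone, that is an event the redo outcome exists to count. It also bears directly on the second research question. Withdrawing the participant for that event makes a post-randomisation exclusion depend on an outcome.

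If withdrawal means removal from the analysis, two things follow. The redo figure can look better than it was. The comparison of app with paper is also no longer between the groups as randomised if withdrawals differ by arm. With about 15 participants per arm, one participant is 1/15 = 6.7% of an arm.

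**Working it through.** The plan gives no redo rate, no rate of consultant revision, and no alpha or power, so there is no figure to reproduce. The check sets the texts side by side and then illustrates the scale.

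**Inputs**
- From the protocol: 30 participants, randomised 1:1, so 30/2 = 15 per arm if exactly balanced.
- Assumed: 3 plans redone among 30, one of them by a psychiatry consultant.
- Assumed: a chance per participant of consultant revision of p = 1%, 3% or 5%.

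**Who counts as clinical staff**
- *Plain reading:* a psychiatry consultant is included. The withdrawal rule then overlaps with the redo outcome.
- *Narrow reading:* Description of interventions, having named the psychiatric nurse or social worker, says "These clinical providers must approve all safety plans in this study". The supervision section explains ED clinical staff in the same way. Consultant revisions would then be counted nowhere, yet the participant still leaves the study.

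**Effect on the overall redo proportion if the withdrawn participant is dropped** (exact Clopper-Pearson 95% intervals)
- All randomised kept: 3/30 = 10.0% (2.1 to 26.5).
- Plain reading: (3 − 1)/(30 − 1) = 2/29 = 6.9% (0.8 to 22.8).
- Narrow reading: 3/(30 − 1) = 3/29 = 10.3% (2.2 to 27.4).
- Two participants handed over to clinical staff and dropped, with no redo among them: 3/(30 − 2) = 3/28 = 10.7% (2.3 to 28.2).

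**Effect by arm, plain reading, starting from 2/15 versus 1/15** (13.3% − 6.7% = 6.7 points)
- Dropped case in the first arm: 1/14 versus 1/15, 7.1% − 6.7% = 0.5 points.
- Dropped case in the second arm: 2/15 versus 0/14, 13.3% − 0% = 13.3 points.

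The difference can shrink or grow, so the direction of any between-arm bias is unknown.

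**Chance of at least one consultant revision among 30**, 1 − (1 − p)^30, with 30p events expected
- p = 1%: 26.0%, 0.3 events.
- p = 3%: 59.9%, 0.9 events.
- p = 5%: 78.5%, 1.5 events.

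The documents do not favour any of these values. They say only that the event is unlikely.

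**The case against.** The strongest case against the point has five parts.

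- **Necessity against choice.** The outcome counts plans that must be redone, whereas the withdrawal rule covers what consultants may choose to do, down to an edit. This stands. An edit is not a redo, and the fix should not pool the two.
- **The narrow reading has textual support.** Approval belongs to the nurse or social worker, and the section on safety plan quality attaches no withdrawal to plans modified at that step. This also stands. It limits the loss to the consultant route, but it leaves consultant revisions uncounted.
- **A reader might infer that withdrawn participants' data are discarded.** The documents do not say so. The redo measure is a number to be tracked, with no stated denominator. The consent form and Figure 2 are not visible and may deal with data after withdrawal. What remains is a withdrawal rule tied to an outcome, with no visible text that offsets it.
- **A reader might infer a bias towards one arm.** The two by-arm examples rule that out as a general claim. Data Analysis also does not name a by-arm comparison of redone plans; only satisfaction is specified for each method.
- **The event is called unlikely, and this is a pilot without a sample size calculation.** True, and the intervals above overlap almost entirely. But whether plans satisfy clinical personnel is one of the pilot's own questions, and the cost of settling the matter is very low.

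Restricting the quality score to completed plans is the protocol's stated choice and is not criticised here.

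**Conclusion.** The point holds in a limited form. A participant can be withdrawn after randomisation because of an event that bears on the second research question and, where a consultant had to redo the plan, falls within the ordinary meaning of the redo outcome. The rule for planning not completed with a peer adds a second withdrawal after randomisation. No visible text keeps either group in the analysis.

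On the plain reading, dropping one consultant redo lowers an assumed 10.0% to 6.9%, about 3 points. On the narrow reading the change is 0.3 points upwards. The between-arm effect has no known direction. All redo counts and event rates here are assumptions, and the expected effect is small because the protocol regards the event as unlikely.

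It would go too far to conclude that the redo outcome is emptied or that the plan orders an exclusion from analysis. Modifications at nurse or social worker approval carry no stated withdrawal, and nothing visible says that data are deleted.

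**What to change.** Reconcile the two withdrawal rules (Study Design and Procedures; Supervision and debriefing of peers) with Data Analysis:

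- State that these participants stay in the analysis as randomised, with the data already collected kept: the plan as first submitted, its quality score if the plan was completed, and the satisfaction rating.
- Count plans restarted or redone by a psychiatry consultant in the redo outcome. Report consultant revisions or edits on a separate line. Give both by arm over all randomised participants.
- Report plans not completed with study staff (hand-overs to clinical staff and stops for decompensation) separately, by arm and with the reason.

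The clinical hand-over and stopping rules are not touched.

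The cost is a few sentences and a few reporting rows, with no extra participants. Much of the material is already kept under Data Handling and Recordkeeping. Because the tablet is cleared before each patient, the team should confirm that a copy exists of any app plan that was shown to staff and not emailed. The downside is a slightly less favourable redo figure and a little more reporting.
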